9.3 Randomization and Stratification

Subjects who meet enrollment criteria will be randomized at Week 2 in a 1:1 ratio according to the study treatment that has been randomly assigned to the Patient Number on the Randomization List held by the local site pharmacist. Randomization will be stratified by: (1) type of ART: patients taking any booster (ritonavir or cobicistat) as part of their ART regimen and patients not taking a booster; and (2) known CHD or not.

9.4 Sample size and Accrual

The predicted percent reduction in LDL-c by rosuvastatin dose is as follows: 20mg (55-60%), and 40mg (60-63%). The predicted percent reduction in LDL-c by pravastatin 40mg is 30%. The expected difference in LDL-c for subjects receiving high (rosuvastatin 20-40mg daily) versus moderate (pravastatin 40mg daily) intensity statin doses in this study is therefore approximately 25-30% compared with moderate. In a landmark study of patients with CHD comparing high intensity statin (atorvastatin 80mg, which is similar in intensity of expected lipid lowering to rosuvastatin 20-40mg) versus pravastatin 40mg, mean LDL cholesterol levels during treatment were 62mg/dl and 95mg/dl for high intensity and pravastatin groups (with standard deviations of approximately 20mg/dl), respectively.

Given potentially lower baseline LDL cholesterol levels in this study (we expect mean LDL of participants will be approximately 105, including patients off statin therapy and those on low intensity therapy), realistic expected mean LDL cholesterol levels are 75mg/dl for the pravastatin group and 50mg/dl for the high-intensity/rosuvastatin group. These expected LDL cholesterol levels are similar to those seen in the high intensity versus lower intensity treatment groups in a more recent trial of lipid-lowering strategies in high-risk patients, in which there was no excess of adverse events in the higher-intensity group which achieved a mean LDL of 53.7mg. In order to have a power of 0.80 with a two-sided alpha of 0.05 to detect a 25mg/dl difference in LDL-c lowering with a standard deviation of LDL-c of 20, the desired sample size would be at least 11 cases and 11 controls. Given the potential for study drug discontinuation in an expected 8 or fewer patients (based on on-treatment symptoms being present in 5-20% of patients on statins), the goal subject enrollment for this study is 30 with a possible enrollment of up to 50 participants in order to ensure adequate power.

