3.0 STUDY DESIGN

This is a single center, randomized, controlled, open-label phase II trial. Up to 40 subjects not already on high dose statin therapy who have documented CHD and/or calculated 10-year ASCVD risk >15% will be included and started on moderate dose statin therapy (pravastatin 40mg daily) for an initial two-week run-in period. Subjects not demonstrating significant toxicity at week 2 will then be randomized to rosuvastatin 20mg versus continuing pravastatin 40mg daily. Subjects will return at week 6; those in the rosuvastatin arm who do not demonstrate significant safety or toxicity concerns will then have doses increased to rosuvastatin 40mg (high dose group). The group randomized to pravastatin 40mg daily at week 2 will not have their dose increased at the end of week 6.

The following treatment regimens will be used:

Stage One (Run-in): Pravastatin 40mg daily (Weeks 0-2),

Stage Two (Randomization in 1:1 ratio):

- Moderate intensity group: Pravastatin 40mg daily (Weeks 2-14)
OR
- High intensity group: Rosuvastatin 20mg daily (Weeks 2-6), potentially titrated to Rosuvastatin 40mg daily (Weeks 6-14).

Total duration of the study is 14 weeks: 2 weeks for the initial run-in, 6 weeks following randomization, and 6 weeks following dose increase.

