4.3 Study Enrollment Procedures

4.3.1 Prior to implementation of this protocol, sites must have the protocol and the protocol consent form approved by their local institutional review board (IRB).

Once a candidate for study entry has been identified, details will be carefully discussed with the subject. The subject will be asked to read and sign the approved protocol consent form.

Candidates for study entry will be identified using an existing IRB-approved data repository of HIV-infected persons in the Northwestern Medicine Enterprise Data Warehouse (NMEDW). These candidates will be identified by querying this NMEDW data repository for any living HIV-infected persons aged 18 to 75 who have no HIV viral RNA values of 400 copies/ml or greater anytime in the previous 12 months from the time of screening and who have any diagnosis of coronary heart disease (CHD) based on any documented ICD-9-CM codes 410-414 and/or ICD-10-CM codes I21-I25. Candidates will also be identified by calculating the 10-year ASCVD risk of patients referred by primary care providers. Once these candidates are identified, participants will be excluded if they are noted to be prescribed atorvastatin 20mg daily or greater, rosuvastatin 10mg daily greater, atazanavir/ritonavir (at any dose), lopinavir/ritonavir (at any dose), simeprevir.(at any dose), or are not currently taking antiretroviral therapy. Of the remaining candidates, persons with an active primary care provider and/or infectious disease provider at Northwestern Medicine will be eligible to be contacted for enrollment via telephone. The order of contacting patients will be by those with the most recent new diagnoses of CHD first, with the plan to continue contacting patients (those with the earlier CHD diagnosis dates would be contacted later, then patients with no known CHD but with 10-year ASCVD risk of 15% or greater) until the target enrollment is achieved.

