6.2.4 Discontinuation Evaluations

Evaluations for Registered Subjects Who Do Not Start Study Treatment

Subjects who do not begin study treatment should have screening and entry forms completed and entered in the database. Beyond the entry visit, no further evaluations are required. These subjects will be replaced.

Premature Treatment Discontinuation Evaluations

Subjects who discontinue the study medications before the end of the study (Week 14) should have the Premature Treatment Discontinuation evaluations done within 7 days after stopping study drugs. They will be encouraged to continue to attend all study visits and receive study evaluations as per section 6.1 through Week 14.

Premature Study Discontinuation Evaluations

All subjects who prematurely discontinue participation in the study should have the Premature Study Discontinuation evaluations done.

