8.2 Premature Study Discontinuation

- Request by the subject to withdraw
- Request of the primary care provider or investigator if s/he thinks the study is no longer in the best interest of the subject
- Subject judged by the investigator to be at significant risk of failing to comply with the provisions of the protocol as to cause harm to self or seriously interfere with the validity of the study results
- At the discretion of the IRB, FDA, IND sponsor, or pharmaceutical supporters

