9.0 STATISTICAL CONSIDERATIONS

9.1 General Design Issues

HILLCLIMBER is a randomized, controlled, open-label phase II trial. 40 subjects not already on high dose statin therapy who have CHD and/or calculated 10-year ASCVD risk >15% will be included and started on moderate dose statin therapy (pravastatin 40mg daily) for an initial two-week run-in period. Subjects not demonstrating significant toxicity at week 2 will then be randomized to high intensity statin therapy (rosuvastatin 20mg) versus continuing moderate intensity statin therapy (pravastatin 40mg daily). At week 6, subjects in the rosuvastatin arm who do not demonstrate significant toxicity and whose LDL-c is >60mg/dl and decreased by less than 25% compared with week 2 will then have doses increased to rosuvastatin 40mg (high dose group). Efficacy and safety will be evaluated at Week 14.

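### The enrolment target differs between sections (40, up to 40, or a goal of 30 and possibly 50), and the goal of 30 appears to rest on a discontinuation allowance that does not match the intention-to-treat analysis

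*Combined protocol and SAP*

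**What the plan says.** **Enrolment.** The synopsis gives a sample size of 40. Section 9.1 agrees: "40 subjects not already on high dose statin therapy who have CHD and/or calculated 10-year ASCVD risk >15% will be included and started on" the run-in. Section 3.0 sets a ceiling, "Up to 40 subjects not already on high dose statin therapy", and these patients "will be included and started on moderate dose statin therapy (pravastatin 40mg daily) for an initial two-week run-in period". All of this is before randomisation at week 2. Section 9.4 instead states that "the goal subject enrollment for this study is 30 with a possible enrollment of up to 50 participants in order to ensure adequate power".

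**What depends on it.** Section 4.3.1 has candidates contacted "until the target enrollment is achieved". Section 9.5 places the interim safety review when roughly half the patients have completed week 6.

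**Basis of the number.** Section 9.4 asks for at least 11 patients per arm, with power 0.80 and two-sided alpha 0.05, "to detect a 25mg/dl difference in LDL-c lowering with a standard deviation of LDL-c of 20". It then allows for 8 or fewer drug discontinuations, citing symptoms in 5-20% of statin users.

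**Analysis.** Sections 9.2.1 and 9.6.1 define the primary comparison as percent change in LDL-c from week 2 to week 14, by intention to treat. Section 9.6.1 names both logistic regression and two-sample t-tests. Section 9.5 keeps patients stopped by the safety officer in follow-up and in the analysis. For others who stop drug, section 6.2.4 says: "They will be encouraged to continue to attend all study visits". Complete withdrawal from the study is also possible under section 8.2 ("Request by the subject to withdraw").

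**The concern.** A trial needs one recruitment target. Here a team following 9.4 could stop at 30, one following the synopsis would stop at 40, and one using the flexibility in 9.4 could reach 50 in breach of 3.0. In an open-label trial, an unstated trigger for going past the goal leaves room for the decision to be made with knowledge of the results.

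The goal of 30 also seems to be built by adding discontinuers on top of the evaluable number, as if they left the analysis. Under intention to treat, a patient who stops drug but has a week-14 LDL stays in and dilutes the difference. Only a patient without a week-14 value reduces n. The two losses affect power differently, and 9.4 does not separate them.

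Finally, the only power figure is on the mg/dl scale and the endpoint is on the percent scale.

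**Working it through.** **Inputs.** From 9.4: difference 25 mg/dl, SD 20 mg/dl, two-sided alpha 0.05, power 0.80, 8 or fewer discontinuers. From 9.3: 1:1 allocation. From 9.6.1: two-sample t-test, intention to treat.

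**1. The plan's own figure.** n per arm = 2 × (1.96 + 0.84)² × 20² / 25² = 10.05 (unrounded quantiles), rounded up to 11. Noncentral-t power at 11 per arm is 0.796, so the plan's figure reproduces. The goal of 30 matches 2 × 11 + 8 = 30; 9.4 does not spell out this sum.

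**2. Fit of the allowance.** 8/40 = 20%, but 8/30 = 26.7%. The 5-20% in 9.4 is the share of patients with symptoms, not a discontinuation rate. Eight is the top of that range only for a total of 40.

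**3. Power when discontinuers are kept.** Let a fraction f of each arm stop drug, be measured at week 14 and contribute no between-arm difference. The expected difference is (1 − f) × 25, with SD held at 20.

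| Randomised | f = 0 | f = 20% | 8 patients |
|---|---|---|---|
| 30 | 0.91 | 0.75 (20.0 mg/dl) | 0.68 (18.3 mg/dl) |
| 40 | 0.97 | 0.87 (20.0 mg/dl) | 0.87 (same case) |
| 50 | 0.99 | 0.93 (20.0 mg/dl) | 0.95 (21.0 mg/dl) |

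At 30 randomised, power is 0.802 at f = 15% and falls below 0.80 just above that.

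**4. Power when discontinuers are missing instead.** 30 randomised with 20% lacking a week-14 LDL leaves 24 analysed, power 0.83. With 8 missing, 22 are analysed, power 0.796, which is the case the allowance in 9.4 seems to describe.

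**5. Entrants against randomised.** The documents give no run-in loss rate. As an assumption only: if 4 of 40 entrants are lost in the run-in, 36 are randomised, with power 0.95 at f = 0 and 0.83 at f = 20%.

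**6. Interim timing.** 0.5 × 30, 40 and 50 = 15, 20 and 25 patients.

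**7. Percent scale.** Section 9.4 supports several differences, depending on the reading:
- its stated 25-30%;
- its predicted reductions subtracted directly: 55 − 30 = 25 to 63 − 30 = 33 points;
- its expected means: (75 − 50)/75 = 33 points;
- its predicted reductions taken from untreated LDL and re-expressed from a week-2 value after a full pravastatin effect: 1 − 0.45/0.70 = 36 to 1 − 0.37/0.70 = 47 points.

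The range is therefore roughly 25 to 47 points. With no dilution, 30 randomised keep power 0.80 up to an SD of percent change of 23.6 points (difference 25) or about 44 points (difference 47). At 40 randomised the limits are 27.5 and about 52. The documents give no SD of percent change, so these are thresholds, not power estimates.

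**The case against.** - **The plan protects itself by expansion.** Section 9.4 pairs the goal of 30 with up to 50 for the sake of power, so it does not claim that 30 suffices in every case. This stands as far as it goes. But the expansion has no trigger and exceeds the 3.0 ceiling.
- **The adverse case is conservative.** It requires every kept discontinuer to show no between-arm difference at week 14, although section 7.1 allows drug to be resumed after some interruptions. This stands, and 0.75 and 0.68 should be read as that case, not as forecasts.
- **The conflict is narrower than four different numbers.** A ceiling of 40 is compatible with 40 and with a goal of 30, and 3.0 and 9.1 do say that they count patients starting the run-in. Agreed: the real clashes are a goal of 30 against 40, and 50 against the ceiling. Only 9.4 is silent on what it counts.
- **The interim effect is modest.** The review is at approximately half, and its stopping rule is a proportion. Agreed; the consequence is timing and precision.
- **The arithmetic is correct.** Agreed. This is an internal inconsistency.

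A reader might infer that the trial is underpowered, or that the change of scale costs power. The documents support neither. On the plan's inputs 30 randomised give 0.91 without discontinuation, and 40 randomised give 0.87 even with 8 kept discontinuers. If the SD scaled with the mean (20/75 = 26.7 points against 33.3), power would be the same on either scale.

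**Conclusion.** The point holds as an internal inconsistency that should be corrected. The conflict between 9.4 and the synopsis, 3.0 and 9.1 is plain on the page and needs no assumption. It affects when recruitment ends and when the safety review takes place.

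The discontinuation allowance does not match the intention-to-treat plan. The size of this is conditional. With 25 mg/dl, SD 20 and no between-arm difference among kept discontinuers, 30 randomised fall below 0.80 above about 15% discontinuation, while 40 stay above 0.80 with the plan's 8. Reading 22 + 8 as the origin of 30 is an inference from the figures.

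The mg/dl power statement is a documentation gap. Without an SD of percent change, power for the primary test can be neither confirmed nor faulted.

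**What to change.** - **One N.** State a single target in the synopsis, 3.0, 9.1 and 9.4, say that it counts run-in entrants, and give the expected number randomised. Forty already fits three of the four places.
- **Expansion.** Delete the option of 50 from 9.4, or raise the 3.0 ceiling and write in advance a rule for exceeding the target that uses no efficacy data.
- **Power statement in 9.4.** Replace it with wording such as: With [n] of [N] run-in entrants expected to be randomised, the intention-to-treat two-sample t-test of percent change in LDL-c from week 2 to week 14 (two-sided alpha 0.05) has power [range] for a difference of [value, justified from the week-2 on-pravastatin baseline], assuming an SD of percent change of [value, source], [a]% stopping study drug but measured at week 14, and [b]% without a week-14 LDL. The sponsor supplies the bracketed values. The difference should not be fixed from 9.4 as it stands, because its figures allow roughly 25 to 47 points.
- **Section 9.6.1.** Remove the reference to logistic regression for this continuous endpoint, so that the powered test is the planned test.

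**Cost.** Wording only. A target of 40 is 10 above the 9.4 goal, the stated power may become a less favourable range, and the flexibility to reach 50 is lost unless a rule is written.

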9.5 Monitoring

When approximately 50% of patients have completed the study through week 6, an interim analysis for safety will be conducted by an independent data monitoring committee. Patients with levels of CK, AST, ALT at weeks 2, 6, or 10 that are 3 times the upper limit of normal or greater will have the study drug discontinued at that time. If >25% of study enrollees are required to have the study drug discontinued at the interim analysis, the trial will be stopped. Serious adverse events will be monitored by the committee on an ongoing basis throughout the study. If a study patient has CK, AST, or ALT levels of 3 times the upper limit of normal or greater any time prior to the interim safety analysis, the study coordinator will alert the medical safety officer ([name]), who will contact the patient and instruct the patient to immediately discontinue the study drug. Such patients who discontinue the study drug at the

medical safety officer's request will continue to be followed in the study and included in intention-to-treat analyses.

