2.0 Background

This study is a phase II investigation of the efficacy of high intensity versus moderate intensity lipid lowering statin therapy for HIV-infected persons with coronary heart disease (CHD) and/or high risk for atherosclerotic cardiovascular disease (ASCVD) not already on high intensity lipid lowering therapy. This is a pilot study for potential future studies that would be adequately powered to evaluate the safety – in addition to efficacy – of high-intensity versus moderate-intensity statin regimens for HIV-infected persons with CHD and/or high risk for ASCVD. The study drugs (rosuvastatin and pravastatin) are approved and in regular clinical use, but rosuvastatin is being repurposed in this study for a new population in which there are no data for the higher intensity therapy under study.

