5.0 STUDY TREATMENT

5.1 Regimens, Administration, and Duration

After a 2-week pravastatin 40mg daily run-in period, subjects will be randomly assigned to rosuvastatin 20mg daily or pravastatin 40mg daily at week 2 in a 1:1 ratio. At week 6, subjects on the Rosuvastatin arm may have their dose escalated to 40mg daily.

Run-in: Pravastatin 40mg daily for 2 weeks (Weeks 0-2)

Randomization (1:1 ratio) at Week 2:

- Moderate intensity strategy: Pravastatin 40mg once daily for 12 weeks (Weeks 2-14)
OR
- High-intensity strategy: Rosuvastatin 20mg once daily for 4 weeks (Weeks 2 to 6)
 - Continue Rosuvastatin 20 mg once daily (Weeks 6 to 14) if:
 - AST or ALT between 1.5x and 3x ULN
OR
 - CK between 3x and 10x ULN
OR
 - Grade 1 or 2 toxicity attributable to rosuvastatin is present
 - Escalation of Rosuvastatin to 40 mg daily (Weeks 6 to 14) if:
 - AST, ALT, and CK \leq 1.5x ULN at week 6
AND
 - CK \leq 3x ULN at week 6
AND
 - No grade 1 or greater toxicity attributable to rosuvastatin is present

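### The only interim safety look is triggered at week 6, so it guarantees no laboratory data on rosuvastatin 40 mg, and no later aggregate laboratory review is planned

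*Combined protocol and SAP*

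**What the plan says.** Section 9.5 (Monitoring) plans one interim analysis: "When approximately 50% of patients have completed the study through week 6, an interim analysis for safety will be conducted". An independent data monitoring committee conducts it. The one trial-level stopping rule is tied to it: "If >25% of study enrollees are required to have the study drug discontinued at the interim analysis, the trial will be stopped".

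The same section has a per-patient rule that is not limited to the period before the look: "Patients with levels of CK, AST, ALT at weeks 2, 6, or 10 that are 3 times the upper limit of normal" or more lead to discontinuation. It also provides that "Serious adverse events will be monitored by the committee on an ongoing basis throughout the study". A further route, from coordinator to safety officer to patient, covers values of 3 times the upper limit of normal (ULN) or more found "any time prior to the interim safety analysis, the study coordinator will alert the medical safety officer".

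On dose timing, Section 5.1 says: "At week 6, subjects on the Rosuvastatin arm may have their dose escalated to 40mg daily". Section 5.1.1 makes this depend on the week-6 laboratory and toxicity results and allows up to 5 days to notify the patient. The schedule in Section 6.1 and Section 7.1.2 place the next routine CK, AST and ALT at week 10, then week 14.

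**The concern.** Section 2.0 explains why safety matters here: "rosuvastatin is being repurposed in this study for a new population in which there are no data for the higher intensity therapy under study". Section 2.1 puts rosuvastatin 20-40 mg in that untested range, and Section 9.2.1 lists CK and transaminase elevations under its primary endpoints.

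A patient who has just completed week 6 has taken pravastatin throughout, or pravastatin followed by rosuvastatin 20 mg. The trigger can therefore be met, and the >25% rule passed, with no laboratory result from anyone on 40 mg. Section 9.5 names week 10 as a visit that can lead to discontinuation, yet the look does not wait for it. The document describes no later occasion on which the committee sees laboratory toxicity in aggregate.

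**Working it through.** The plan gives no accrual rate and no figure for what the look will contain, so there is no stated number on this point to reproduce.

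**Inputs from the documents.** N = 40 (synopsis and Section 9.1; Section 9.4 says a goal of 30 and up to 50). Allocation 1:1. Trigger at 50% through week 6. First scheduled laboratory tests after escalation at week 10.

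**Assumptions.** Even accrual at r patients per week, no dropout, data cut at the trigger, half of patients on rosuvastatin.

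**Formula.** Patient i enters at (i − 1)/r weeks. The look falls when patient N/2 reaches week 6, at (N/2 − 1)/r + 6 weeks. Patient i has a week-10 result by then if (N/2 − i)/r ≥ 4, that is, if i ≤ N/2 − 4r. At N = 40 this gives 20 − 4r patients, of whom 10 − 2r are on rosuvastatin (never below 0). If a true laboratory event rate of 10% is assumed, the chance of seeing at least one event among m patients is 1 − 0.9^m.

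| Entries per 4 weeks | r per week | Look at (weeks) | Patients with week-10 result | On rosuvastatin (m) | Chance of at least 1 event at 10% |
|---|---|---|---|---|---|
| 2 | 0.5 | 44 | 18 | 9 | 61% |
| 4 | 1 | 25 | 16 | 8 | 57% |
| 8 | 2 | 15.5 | 12 | 6 | 47% |
| 20 | 5 | 9.8 | 0 | 0 | 0% |

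Over rates from 0.5 per week upward, the rosuvastatin count runs from 6.5 down to 0 at N = 30 and from 11.5 down to 0 at N = 50.

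These counts are upper bounds for 40 mg, because not every rosuvastatin patient will be escalated. Section 9.1 adds LDL-c conditions for escalation that Section 5.1 does not have, so the documents do not settle how many would be.

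**With a second table at week 10.** The same 20 patients include about 10 on rosuvastatin with week-10 results, whatever the accrual rate (1 − 0.9^10 = 65%). The gain is 1 patient at 2 per 4 weeks, 4 at 8, and 10 at 20.

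**Who counts toward the >25% rule.** For CK between 3 and 10 times ULN the sections disagree:
- Section 9.5 discontinues drug from 3 times ULN.
- Section 5.1 continues rosuvastatin 20 mg between 3 and 10 times ULN.
- Section 7.1 makes 10 times ULN or more the ground for holding drug.
- Section 7.1.3 grades 3 to below 10 times ULN as Grade 1 or 2, and Section 7.1.1 lets such patients continue.

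The numerator of the stopping rule depends on which of these is followed.

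**The case against.** The strongest reply is that much monitoring does not end at the look. The week-10 discontinuation rule in Section 9.5 has no end date. Section 7.1 requires drug to be held or stopped for defined toxicities, and the protocol chair must be told of toxicities that interrupt or end treatment. The committee follows serious adverse events throughout, and Section 10.4 counts possible drug-induced liver injury as serious, so a suspected liver signal can reach the committee later. A reader might infer that 40 mg goes unmonitored after the interim, or that the lapse of the alert leaves nobody to act. The documents support neither. What remains is the lack of a later aggregate review, felt most for asymptomatic CK rises, which are not serious events in themselves.

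A reader might also infer that the look will hold no 40 mg data. Zero requires about 20 entries per 4 weeks, at a single centre that telephones candidates in sequence (Sections 3.0 and 4.3.1). At slower rates most of the data would be there, and any delay between trigger and data cut would add more. That is fair, but it makes the content of the look depend on accrual instead of on the plan.

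Nor is 40 mg the only untested dose. Section 2.1 covers 20-40 mg, and the week-6 look does examine 20 mg.

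Finally, the pooled rule is insensitive. With 20 enrollees, more than 25% means 6 discontinuations. If the true rate is 30% on rosuvastatin and none occur on pravastatin, P(at least 6 of 10) = 4.7%. With 40 enrollees, P(at least 11 of 20) = 1.7%. This stands: the value of a second look lies mainly in showing the committee the escalated patients, not in the threshold.

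**Conclusion.** The point holds in a limited form. As written, the single formal look and the single application of the >25% rule guarantee no laboratory data on 40 mg, and no later aggregate committee review of laboratory toxicity is described. How much would be missed is uncertain: at N = 40 the look would hold week-10 results for about 9, 6 or 0 rosuvastatin patients at 2, 8 or 20 entries per 4 weeks. That range rests on assumed even accrual, no dropout and a data cut at the trigger, and the number actually on 40 mg would be no higher. Individual safeguards continue, so this is a worthwhile and cheap improvement, not a failure of patient protection.

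The alert wording is a separate, smaller matter. The text does limit it to the period before the interim, but whether it should continue cannot be settled while its CK level conflicts with Sections 5.1, 7.1, 7.1.1 and 7.1.3.

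**What to change.** In Section 9.5, keep the week-6 look. Add that the same committee receives the same tabulation again once those patients have week-10 results, with patients escalated to 40 mg listed separately and the existing >25% rule applied. The cost is one more table and one more committee review, about 4 weeks after the trigger (week 10 minus week 6). No new assessments are needed.

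Separately, reconcile the CK levels in Sections 5.1, 7.1, 7.1.1, 7.1.3 and 9.5, state which discontinuations count toward the >25% rule, and then state whether the safety-officer alert continues after the interim. Simply deleting the alert's time limit is not the answer: it carries an instruction to stop drug, so deletion would extend one side of the unresolved conflict to the whole trial. Reconciling the text is a clinical decision for the sponsor and costs only an amendment of wording.

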4.1.6 Men and women age 18 to 75 years of age

4.1.7 Ability and willingness of subject to provide informed consent

4.2. Exclusion Criteria

- 4.2.1 Serious illness or AIDS-related complication within 21 days of screening requiring systemic treatment and/or hospitalization until candidate either completes therapy or is clinically stable on therapy, in the opinion of the site investigator, for at least 7 days prior to study entry. Need for systemic therapy for malignancy currently or anticipated during the study period.
- 4.2.2 No coronary heart disease (CHD) and 10-year ASCVD risk <15.0%.
- 4.2.3 Not currently receiving antiretroviral therapy or taking any of the following antiretroviral agents: atazanavir/ritonavir, lopinavir/ritonavir, or simeprevir.
- 4.2.4 Not currently receiving any of the following agents: cyclosporine or rifampin.
- 4.2.5 History of statin intolerance leading to discontinuation, dose decrease, or change to less potent dose equivalent
- 4.2.6 Statin absolute contraindication
- 4.2.7 Current use of atorvastatin 20mg daily or greater or rosuvastatin 10mg daily or greater
- 4.2.8 Chronic kidney disease stage 4 or greater (including dialysis)
- 4.2.9 Systolic heart failure with last documented LVEF <35%
- 4.2.10. Pregnant or breastfeeding
- 4.2.11. Laboratory values obtained within 45 days prior to study entry:
 - LDL-c <80 mg/dl while not on statin or LDL-c <60 mg/dl while on statin
 - ALT > 3 x Upper Limit of Normal (ULN)
 - AST > 3 x ULN
 - Creatinine kinase (CK) > 10 x ULN
 - Calculated creatinine clearance (CrCl) <50 mL/min, as estimated by the Cockcroft-Gault equation
- 4.2.12. Life expectancy <12 months
- 4.2.13. Prior organ transplant
- 4.2.14. Active malignancy
- 4.2.15. Inflammatory muscle disease

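### For a rosuvastatin patient with week-6 CK of 3 to <10x ULN, Section 5.1 says continue 20 mg and Section 9.5 says stop, with no rule on which prevails

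*Combined protocol and SAP*

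**What the plan says.** Section 9.5 (Monitoring) applies one limit to three analytes. It names "Patients with levels of CK, AST, ALT at weeks 2, 6, or 10 that are 3 times the upper limit of normal or greater" and requires their study drug to be discontinued. A second sentence covers any such value before the interim safety analysis: the coordinator alerts the medical safety officer, "who will contact the patient and instruct the patient to immediately discontinue the study drug". Patients stopped this way "will continue to be followed in the study and included in intention-to-treat analyses".

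Section 5.1 governs the week-6 decision in the rosuvastatin arm. Under the instruction "Continue Rosuvastatin 20 mg once daily (Weeks 6 to 14) if" it gives three alternative conditions: AST or ALT between 1.5x and 3x ULN, "CK between 3x and 10x ULN", or a Grade 1 or 2 toxicity attributable to rosuvastatin. Section 5.1.1 adds that after the week-6 results these patients are told either to take two tablets or to stay on one. It mentions no third outcome.

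Section 7 uses 10x ULN for CK. Section 7.1 makes CK of 10x ULN or more a Grade 3 event and a reason to hold drug. The table in 7.1.3 grades 3 to <6x as Grade 1 and 6 to <10x as Grade 2, and 7.1.1 allows Grade 1 or 2 toxicity to continue. Section 8.1 refers to Section 7, not to 9.5, for toxicity that ends treatment.

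**The concern.** The issue is not whether 3x or 10x ULN is the better CK limit. It is that one laboratory value, at one visit, in one arm, has two opposite written instructions. Staff working from the treatment section would keep the patient on rosuvastatin 20 mg for eight more weeks. Staff working from the monitoring section would stop the drug.

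This matters for safety because CK is the protocol's laboratory marker of muscle toxicity, and Section 2.1 says no trial has tested these rosuvastatin doses in this population. It matters for the analysis because drug discontinuation related to adverse events is a safety endpoint in 9.2.1 and time to discontinuation is analysed in 9.6.2. Both would depend partly on which section was followed. Patients who are stopped also stay in the primary LDL-c comparison.

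**Working it through.** **Step 1. Instructions for CK of 3 to <10x ULN, side by side.**

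| Section | Applies to | Instruction |
|---|---|---|
| 9.5, first rule | both arms, weeks 2, 6 and 10 | discontinue |
| 9.5, second rule | both arms, any time before the interim | discontinue immediately |
| 5.1 | rosuvastatin arm, week 6 | continue 20 mg to week 14 |
| 7.1, 7.1.1, 7.1.3 | both arms, any visit | Grade 1 or 2; may continue |

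The 9.5 and 5.1 rows are both directive and cannot both be obeyed. The Section 7 row is permissive, so a mandatory 9.5 rule could coexist with it. The direct contradiction is therefore confined to the rosuvastatin arm at week 6. It does not lapse after the interim, because the first 9.5 rule has no such time limit.

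**Step 2. Can 5.1 be read as subordinate to 9.5?** Suppose 9.5 always overrides and 5.1 only sets the dose for those still on drug. The AST/ALT condition in 5.1 (1.5x to 3x ULN) then still has patients to apply to, because 9.5 acts only from 3x. The CK condition (3x to 10x ULN) has none: every value in its range is already at or above the 9.5 limit. That reading leaves a written instruction with nothing to govern.

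**Step 3. Is there a precedence rule?** The only wording of that kind is in 7.1, on how the general guidelines relate to toxicities discussed specifically. It works within Section 7 and does not rank 5.1 against 9.5.

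**Step 4. Effect on the discontinuation endpoint.** One patient changes an arm's incidence by 100/n percentage points. The synopsis gives 40 subjects; Section 9.4 gives a goal of 30 and a maximum of 50.

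- 40 subjects, 20 per arm: 100/20 = 5.0 points
- 30 subjects, 15 per arm: 100/15 = 6.7 points
- 50 subjects, 25 per arm: 100/25 = 4.0 points

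A week-6 stop counts, since 9.2.1 excludes only the initial two weeks.

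**Step 5. Effect on the primary endpoint: illustration only.** Section 9.4 expects mean LDL-c of 105 mg/dl at enrollment, 75 on pravastatin and 50 on rosuvastatin. Assume 75 at week 2.

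- Kept on rosuvastatin: (50 − 75)/75 = −33.3%.
- Stopped, LDL-c back to 105 by week 14: (105 − 75)/75 = +40.0%. The difference is 73.3 points, and 73.3/20 = 3.7 points on the arm mean (4.9 at 15 per arm, 2.9 at 25).
- Stopped, half return to 77.5: (77.5 − 75)/75 = +3.3%. The difference is 36.7 points, and 36.7/20 = 1.8 points.
- Stopped, equally potent statin started in clinical care: about 0.

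The value 105 is a mean over patients on and off statins, so it is not an off-statin level and 3.7 is not an upper bound. The documents give no rate of CK in this band. No size is claimed for this effect.

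**The case against.** The strongest reply is that the conflict is narrow and that cautious staff would follow the stricter rule. The first half stands: it is one arm at one visit, and Section 7 only permits continuation. The second half does not, because no section tells staff to take the stricter rule, and Step 2 shows what that would do to 5.1.

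A reader might infer more from the same text. Three such inferences are not supported.

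- **Eligibility.** Section 4.2.11 excludes "Creatinine kinase (CK) > 10 x ULN", so a patient could enter at 5x ULN and be stopped under 9.5 by week 2. An entry limit need not equal an on-treatment stopping limit. Week 2 is also the point at which patients with significant toxicity are not randomized. This is not a contradiction.
- **A gap at CK 1.5x to 3x ULN.** Escalation in 5.1 requires AST, ALT and CK to be at or below "1.5x ULN at week 6", while the CK condition for continuing begins at 3x. An isolated CK of 2x might seem to meet neither rule. Section 5.1.1 settles it: a patient who does not escalate stays on one tablet. Dropping CK from the 1.5x line would loosen the dosing rule, not repair it.
- **The stopping rule.** Section 9.5 says "If >25% of study enrollees are required to have the study drug discontinued at the interim analysis, the trial will be stopped". A reader might conclude that the count is undefined or that the conflict could reverse the decision. Section 9.5 defines its own event, and a patient it requires to stop counts whether or not staff acted.

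It can also be said that 9.5 and Section 7 differ in more than the CK number: Section 7 holds drug, can allow resumption and considers attribution, whereas 9.5 simply discontinues. That is true, and aligning the CK threshold does not resolve it.

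**Conclusion.** The contradiction holds as a matter of text and rests on no calculation. For a rosuvastatin patient with a week-6 CK of 3 to <10x ULN, Sections 5.1 and 9.5 give opposite orders and neither yields to the other. A safety rule that cannot be followed as written should be corrected.

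The size that can be stated is 5.0 percentage points of discontinuation incidence per affected patient at 20 per arm (6.7 at 15, 4.0 at 25), assuming equal arms. How many patients would be affected is unknown. CK above 3x ULN is a listed safety item in 9.2.1 under either rule, so the ambiguity concerns treatment and discontinuation, not whether the CK elevation is an endpoint.

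A reader might infer that the primary LDL-c result is materially biased. The documents do not support that: the shift in Step 5 depends on an assumed rebound and on what statin, if any, is taken afterwards, and it can be about zero.

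**What to change.** Use one on-treatment CK threshold in Sections 5.1, 7.1, 7.1.3 and 9.5. The investigators should choose between two options on clinical grounds.

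- **Option A, matching 5.1 and Section 7.** In both 9.5 sentences, replace the shared 3x limit with CK ≥10x ULN, or AST or ALT ≥3x ULN.
- **Option B, if 3x ULN is intended for CK.** Delete the 5.1 continuation for CK between 3x and 10x ULN and lower the Section 7 CK hold threshold to 3x ULN. State also that the Grade 1 or 2 continuation in 5.1 and 7.1.1 does not cover CK in this band; otherwise the conflict returns through the grading table.

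Leave 4.2.11 and the 5.1 escalation criteria as they are. The cost is amendment wording and a notice to the monitoring committee, with no added visits, tests or patients. The notice matters most under Option A, because CK of 3 to <10x ULN would then no longer count as a required discontinuation toward the 25% rule.
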